1.2 Display digits

Term	Definition
Percentage (%)	Percentage of patients with or percentage of adverse events or adverse drug reactions, etc.: The obtained value should be rounded off to two decimal places. Other: The obtained value should be rounded off to one decimal place.
Summary statistics	Mean, median, 25th percentile and 75th percentile: The raw data should be rounded off to one decimal place. Standard deviation: The raw data should be rounded off to two decimal places. Minimum and maximum: The same display digit as the one used for the corresponding data will be used.
P value	The obtained value should be rounded down to three decimal places. If the value is less than 0.001 after rounding down to three decimal places, it should be displayed as “p<0.001.”

1.3 Level of significance and confidence coefficient

Level of significance: Two-sided 5%

Confidence coefficient: Two-sided 95%

1.4 Handling of test data

Test data will be handled according to the criteria shown below. If there are multiple data for the same criterion, the one with the test date being closest to the date of protocol-specified assessment should be used. If there is no difference in the number of days from the date of protocol-specified assessment, the later value should be used.

The number of days after the date of the initial dose of Adcetris is defined as 1 for the date of the initial dose of Adcetris and 0 for the day before the date of the initial dose of Adcetris.

Time point for testing	Date of protocol-specified assessment	Acceptable time window
At the initial dose of Adcetris	Date of the initial dose of Adcetris	-15 days to the date of the initial dose of Adcetris
After 1 cycle	
 If Cycle 2 is initiated: Date of Cycle 2 If Cycle 2 is not initiated: 21 days after the date of the initial dose of Adcetris 	
 If Cycle 2 is initiated: Date of Cycle 2 If Cycle 2 is not initiated: 21 days after the date of the initial dose of Adcetris

Time point for testing	Date of protocol-specified assessment	Acceptable time window
After 2 cycles	
 • If Cycle 3 is initiated: Date of Cycle 3 • If Cycle 3 is not initiated: 21 days after the date of Cycle 2 	
 • If Cycle 3 is initiated: From the day after the date of Cycle 2 to the day of Cycle 3 • If Cycle 3 is not initiated: From the day after the date of Cycle 2 to 21 days after the date of Cycle 2
After 3 cycles	
 • If Cycle 4 is initiated: Date of Cycle 4 • If Cycle 4 is not initiated: 21 days after the date of Cycle 3 	
 • If Cycle 4 is initiated: From the day after the date of Cycle 3 to the day of Cycle 4 • If Cycle 4 is not initiated: From the day after the date of Cycle 3 to 21 days after the date of Cycle 3
After 4 cycles	
 • If Cycle 5 is initiated: Date of Cycle 5 • If Cycle 5 is not initiated: 21 days after the date of Cycle 4 	
 • If Cycle 5 is initiated: From the day after the date of Cycle 4 to the day of Cycle 5 • If Cycle 5 is not initiated: From the day after the date of Cycle 4 to 21 days after the date of Cycle 4
After 5 cycles	
 • If Cycle 6 is initiated: Date of Cycle 6 • If Cycle 6 is not initiated: 21 days after the date of Cycle 5 	
 • If Cycle 6 is initiated: From the day after the date of Cycle 5 to the day of Cycle 6 • If Cycle 6 is not initiated: From the day after the date of Cycle 5 to 21 days after the date of Cycle 5
After 6 cycles	
 • If Cycle 7 is initiated: Date of Cycle 7 • If Cycle 7 is not initiated: 21 days after the date of Cycle 6 	
 • If Cycle 7 is initiated: From the day after the date of Cycle 6 to the day of Cycle 7 • If Cycle 7 is not initiated: From the day after the date of Cycle 6 to 21 days after the date of Cycle 6
After 7 cycles	
 • If Cycle 8 is initiated: Date of Cycle 8 • If Cycle 8 is not initiated: 21 days after the date of Cycle 7 	
 • If Cycle 8 is initiated: From the day after the date of Cycle 7 to the day of Cycle 8 • If Cycle 8 is not initiated: From the day after the date of Cycle 7 to 21 days after the date of Cycle 7

Time point for testing	Date of protocol-specified assessment	Acceptable time window
After 8 cycles	
 • If Cycle 9 is initiated: Date of Cycle 9 • If Cycle 9 is not initiated: 21 days after the date of Cycle 8 	
 • If Cycle 9 is initiated: From the day after the date of Cycle 8 to the day of Cycle 9 • If Cycle 9 is not initiated: From the day after the date of Cycle 8 to 21 days after the date of Cycle 8
After 9 cycles	
 • If Cycle 10 is initiated: Date of Cycle 10 • If Cycle 10 is not initiated: 21 days after the date of Cycle 9 	
 • If Cycle 10 is initiated: From the day after the date of Cycle 9 to the day of Cycle 10 • If Cycle 10 is not initiated: From the day after the date of Cycle 9 to 21 days after the date of Cycle 9
After 10 cycles	
 • If Cycle 11 is initiated: Date of Cycle 11 • If Cycle 11 is not initiated: 21 days after the date of Cycle 10 	
 • If Cycle 11 is initiated: From the day after the date of Cycle 10 to the day of Cycle 11 • If Cycle 11 is not initiated: From the day after the date of Cycle 10 to 21 days after the date of Cycle 10
After 11 cycles	
 • If Cycle 12 is initiated: Date of Cycle 12 • If Cycle 12 is not initiated: 21 days after the date of Cycle 11 	
 • If Cycle 12 is initiated: From the day after the date of Cycle 11 to the day of Cycle 12 • If Cycle 12 is not initiated: From the day after the date of Cycle 11 to 21 days after the date of Cycle 11
After 12 cycles	
 • If Cycle 13 is initiated: Date of Cycle 13 • If Cycle 13 is not initiated: 21 days after the date of Cycle 12 	
 • If Cycle 13 is initiated: From the day after the date of Cycle 12 to the day of Cycle 13 • If Cycle 13 is not initiated: From the day after the date of Cycle 12 to 21 days after the date of Cycle 12
After 13 cycles	
 • If Cycle 14 is initiated: Date of Cycle 14 • If Cycle 14 is not initiated: 21 days after the date of Cycle 13 	
 • If Cycle 14 is initiated: From the day after the date of Cycle 13 to the day of Cycle 14 • If Cycle 14 is not initiated: From the day after the date of Cycle 13 to 21 days after the date of Cycle 13

Time point for testing	Date of protocol-specified assessment	Acceptable time window
After 14 cycles	
 • If Cycle 15 is initiated: Date of Cycle 15 • If Cycle 15 is not initiated: 21 days after the date of Cycle 14 	
 • If Cycle 15 is initiated: From the day after the date of Cycle 14 to the day of Cycle 15 • If Cycle 15 is not initiated: From the day after the date of Cycle 14 to 21 days after the date of Cycle 14
After 15 cycles	
 • If Cycle 16 is initiated: Date of Cycle 16 • If Cycle 16 is not initiated: 21 days after the date of Cycle 15 	
 • If Cycle 16 is initiated: From the day after the date of Cycle 15 to the day of Cycle 16 • If Cycle 16 is not initiated: From the day after the date of Cycle 15 to 21 days after the date of Cycle 15

1.5 Handling of missing data

- As a general rule, missing data will not be imputed.
- In the analysis of the frequency qualitative variables, missing data will be handles as “unknown.” In the analysis of summary statistics of quantitative variables, missing data will be excluded.

1.6 Others

- In the analysis for the preparation of documents for the Final Survey Report (final analysis), MedDRA version 19.1 will be used for adverse events, concurrent illness, and past history.
- If a patient has multiple data for a single laboratory test and date of testing, the mean value will be calculated for the analysis of laboratory test results.
- If the date of diagnostic imaging for the assessment of the best response is missing, it will be handled as missing.

2.0 Patient Disposition (Patient Disposition Diagram)

(1) Analysis set to be used

Patients registered

(2) Data to be analyzed

Data to be analyzed includes the numbers of patients registered, institutions with patients registered, patients whose case report forms are available/not available, fixed/non-fixed patients, patients included in/excluded from the safety analysis set, and patients included in/excluded from the efficacy analysis set.

For the number of institutions with patients registered, the same institutions with different departments should not be counted more than once.

For patients whose case report forms are not available, the number of patients by reason for unavailability will be calculated. The reason for unavailability should be transfer or health problems of the investigator or other.

For patients included in safety evaluation, the number of patients by primary disease (Hodgkin's or anaplastic large-cell lymphoma or other) and the overall number of patients will be calculated. For patients included in efficacy evaluation, the number of patients by primary disease (Hodgkin's or anaplastic large-cell lymphoma) and the overall number of patients will be calculated.

For patients excluded from the safety/efficacy analysis set, the number of patients by reason for exclusion will be calculated, and a patient list will be generated.

The selection of patients to be included in safety evaluation and those who are to be included in efficacy evaluation will be made as shown below:

Criterion	Safety evaluation	Efficacy evaluation
Adcetris has never been administered [found afterwards]	×	×
No data for safety evaluation (data to determine the presence or absence of adverse events) are available	×	×
Non-primary disease	○	×

○: Included, ×: Excluded

(3) Figure/table number

Figure 2.0 and Table2.0

3.0 Patient Demographics and Baseline Characteristics

3.1 Patient Demographics and Baseline Characteristics

(1) Analysis sets to be used

Safety analysis set, safety analysis set (Hodgkin’s lymphoma), and safety analysis set (anaplastic large-cell lymphoma)

(2) Data to be analyzed

For each data item, patients will be stratified into the categories below, and the frequency will be calculated. In addition, summary statistics of continuous variable will be calculated:

Data item	Category
Sex	Male or female
Age	<18 years, 18 to 39 years, 40 to 64 years, 65 to 74 years, or ≥75 years
	<18 years, 18 to 64 years, 65 to 74 years, or ≥75 years
Disease duration	<1 year, <1 to 3 years, <3 to 5years, ≥5 years, or unknown
Diagnosis	Hodgkin’s or anaplastic large-cell lymphoma or other
Status	Relapsed/refractory, or new-onset
CD30	Positive, negative, or not measured
Site(s) of involvement	Lymph node, spleen, liver, lung, bone, central nerve, bone marrow, skin, and/or other
ALK (for patients with anaplastic large-cell lymphoma)	Positive, negative, or unknown
Clinical stage	I, II, III, IV, or unknown
B symptoms	Absent or present
ECOG Performance Status	0, 1, 2, 3, or 4
Therapeutic category	Outpatient, inpatient, or unknown
Hypersensitivity disposition	Absent, present, or unknown
Specific hypersensitivity disposition(s)	Medications, food allergy, and/or other
HCV antibody	Negative, positive, or unknown
HBs antigen	Negative, positive, or unknown
HBs antibody	Negative, positive, or unknown
HBV DNA	Negative, positive, or unknown
Past history of pulmonary disorders	Absent or present
Concurrent pulmonary disorders	Absent or present

Data item	Category
Past history of malignant tumours	Absent or present
Concurrent malignant tumours	Absent or present
Past history (other than pulmonary disorders and malignant tumours)	Absent, present, or unknown
Concurrent illness (other than pulmonary disorders and malignant tumours)	Absent or present
Specific concurrent illness(es) (other than pulmonary disorders and malignant tumours)	Diabetes mellitus, hypertension, dyslipidaemia, hyperuricaemia, hepatic disease(s), renal disease(s), infections, peripheral nerve disorders, and/or other
Past history (other than pulmonary disorders and malignant tumours)	Absent, present, or unknown
Concurrent hepatic disorders	Absent or present
Grade of hepatic disorder (Grade based on AST and ALT levels)	None, Grade 1, Grade 2, \geq Grade 3, or unknown
Concurrent renal disorders	Absent or present
Grade of renal disorder (Grade based on serum creatinine)	None, Grade 1, Grade 2, \geq Grade 3, or unknown
Concurrent peripheral neuropathy	None, Grade 1, Grade 2, Grade 3, Grade 4, or unknown
Weight	<40 kg, <40 to 50 kg, <50 to 60 kg, <60 to 70 kg, or \geq 70 kg
BMI	<18.5 kg/m ² , <18.5 to 25 kg/m ² , <25 to 30 kg/m ² , or \geq 30 kg/m ²
Smoking history	Never, current, past, or unknown

Data item	Category
Prior drug therapy	Absent or present
Prior drug therapy regimen(s)	ABVD, CHOP, and/or other (If more than one drug therapies in the same regimen is used in the same patient, it will be counted as one patient.)
Number of prior drug therapy regimens	-
Days from the month of the completion of the final regimen of prior drug therapy to the date of 1 cycle of treatment with Adcetris (Prior drug therapy: Yes)	-
Prior radiotherapy	Absent or present
Days from the month of the completion of the most recent prior radiotherapy to the date of 1 cycle of treatment with Adcetris (Prior radiotherapy: yes)	-
Prior hematopoietic stem cell transplantation	Absent, present (autologous), present (homologous), present (autologous and homologous), or unknown
Other prior therapies	Absent, present, or unknown
Pregnancy during the observation period (for females only)	Absent or present

(3) Figure/table number
Tables 3-1 to 3.1-3

3.2 Prior drug therapy (details)

(1) Analysis sets to be used

Patients included in safety evaluation and patients included in safety evaluation (Hodgkin's

lymphoma) or patients included in safety evaluation (anaplastic large-cell lymphoma)

(2) Data to be analyzed

For prior drug therapy, patients will be stratified into the categories below, and the frequency will be calculated. The percentage of prior drug therapy will be calculated using the number of patients with prior drug therapy as the denominator. In addition, specific prior drug therapies and their percentages will be presented in a pie chart:

Data item	Category
Specific prior drug therapy(ies)	ABVD, CHOP, BEACOPP, C-MOPP, CHASE, CHOEP, DeVIC, EPOCH, ESHAP, GCD, GDP, GEM, ICE, THP-COP, or other (If more than one drug therapies in the same regimen is used in the same patient, it will be counted as one patient.) Prior drug therapies should be listed in descending order of the number of patients. However, "Other" should be listed lastly.

(3) Figure/table number

Tables 3.2-1 to 3.2-3 and Figures 3.2-1 to 3.2-3

4.0 Treatment Given

4.1 Treatment given

(1) Analysis sets to be used

Safety analysis set, safety analysis set (Hodgkin’s lymphoma), and safety analysis set (anaplastic large-cell lymphoma)

(2) Data to be analyzed

For each data item, patients will be stratified into the following categories below, and the frequency will be calculated. In addition, summary statistics of continuous variable will be calculated:

Data item	Category
Initial dose of Adcetris	<1.2 mg/kg, 1.2 mg/kg, >1.2 mg/kg to <1.8 mg/kg, 1.8 mg/kg, or >1.8 mg/kg
Mean dose of Adcetris	<1.2 mg/kg, 1.2 mg/kg, >1.2 mg/kg to <1.8 mg/kg, 1.8 mg/kg, or >1.8 mg/kg
Dose of Adcetris per 3 weeks	<1.2 mg/kg, 1.2 mg/kg, >1.2 mg/kg to <1.8 mg/kg, 1.8 mg/kg, or >1.8 mg/kg
Duration of treatment with Adcetris	1, 2, 3, 4, 5, 6, 7, 8, 9, 10, 11, 12, 13, 14, 15, 16, or ≥ 17 cycles
Reason(s) for discontinuation of Adcetris	Treatment goal achieved, adverse event(s), lost to follow-up, transfer to another hospital, pregnancy, inadequate response, and/or other
Post-baseline hematopoietic stem cell transplantation	Absent, present, or unknown
Type of post-baseline hematopoietic stem cell transplantation	Autologous or homologous
Days from the date of the last dose of Adcetris to hematopoietic stem cell transplantation (autologous) (Post-baseline hematopoietic stem cell transplantation: autologous)	-
Duration of treatment with Adcetris prior to	-

hematopoietic stem cell transplantation (autologous) (Post-baseline hematopoietic stem cell transplantation: autologous)	
Days from the date of the last dose of Adcetris to hematopoietic stem cell transplantation (homologous) (Post-baseline hematopoietic stem cell transplantation: homologous)	-
Duration of treatment with Adcetris prior to hematopoietic stem cell transplantation (homologous) (Post-baseline hematopoietic stem cell transplantation: homologous)	-
Drug(s) other than Adcetris used for the treatment of the primary disease	Absent or present
Drug(s) used for the prevention of infection	Absent or present
Specific drug(s) used for the prevention of infection	Antibiotics/synthetic antibacterial agents, antifungals, antivirals, trimethoprim-sulfamethoxazole combinations, and/or other prophylactics against infections

(3) Figure/table number

Tables 4.1-1 to 4.1-3

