## 5.0 Dosage Regimen

The usual adult dosage is 1.8 mg/kg (body weight) of brentuximab vedotin (recombinant) infused intravenously once every three weeks. The dose should be adjusted depending on the patient's condition.

See the "PRECAUTIONS" section of the package insert.

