## 7.0 Methods

### 7.1 Observation period

From the start of treatment with Adcetris until the completion of 16 cycles [3 weeks per cycle]

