Patients with the onset of infection	Patients with adverse drug reactions that fall under the category of MedDRA SOC Code 10021881 (Infections and infestations)
Patients with the onset of bacterial infection	Patients with adverse drug reactions that fall under the category of MedDRA HLTG Code 10004018 (Bacterial infection), 10008555 (Chlamydial infection), 10028474 (Mycoplasma infection) or 10039135 (Rickettsia infection)
Patients with the onset of fungal infection	Patients with adverse drug reactions that fall under the category of MedDRA HLTG Code 10017528 (Fungal infection)

Term	Definition										
Patients with the onset of viral infection	Patients with adverse drug reactions that fall under the category of MedDRA HLG Code 10047438 (Viral infection)										
Age	
If the month and day of the initial dose of Adcetris is < the month and day of birth, the patient's age will be calculated using the following formula: Year of the initial dose of Adcetris – year of birth – 1.
 
If the month and day of the initial dose of Adcetris is ≥ the month and day of birth, the patient's age will be calculated using the following formula: Year of the initial dose of Adcetris – year of birth.
 
If the month and day of birth are unknown, they should be “January 1,” and if the day of birth is unknown, it should be the first day of the month.
 
If the day, month, and year of birth are unknown but the patient's age is known, the patient's age should be used as it is.
										
BMI	BMI should be calculated using the following formula: Weight (kg)/(0.0001 × height (cm) × height (cm)). The obtained value should be rounded off to one decimal place.										
Disease duration	
The disease duration should be calculated using the following formula: [“Date of the initial dose of Adcetris” – “date of diagnosis of Hodgkin's or anaplastic large-cell lymphoma” +1]/365.25.
 
The day of diagnosis should be the first day of the month provided. If the month of diagnosis is unknown, the date of diagnosis should be “January 1st” of the year provided.
										
Mean dose of Adcetris	Is calculated as the total value of each dose of Adcetris given at each treatment cycle divided by the number of cycles.										

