Dose of Adcetris per 3 weeks	
Is calculated using the following formula: Total “dose of Adcetris”/([“date of the last dose of Adcetris” – “date of the initial dose of Adcetris” + 21)/21].
 
If only 1 cycle of treatment is given, the “date of the last dose of Adcetris” and the “date of the initial dose of Adcetris” should be regarded as the same.
										
Degree of decreased neutrophil count at baseline	
The neutrophil count at baseline will be classified as shown in the table below. If the neutrophil count at baseline is missing, the degree of the neutrophil count at baseline should be handled as missing:
 
  
 No decrease	≥2,000 /mm³	
 
 Grade 1	≥1,500 to <2,000 /mm³	
 
 Grade 2	≥1,000 to <1,500 /mm³	
 
 Grade 3	≥500 to <1,000 /mm³	
 
 Grade 4	<500 /mm³	
  
	No decrease	≥2,000 /mm ³	Grade 1	≥1,500 to <2,000 /mm ³	Grade 2	≥1,000 to <1,500 /mm ³	Grade 3	≥500 to <1,000 /mm ³	Grade 4	<500 /mm ³
No decrease	≥2,000 /mm ³										
Grade 1	≥1,500 to <2,000 /mm ³										
Grade 2	≥1,000 to <1,500 /mm ³										
Grade 3	≥500 to <1,000 /mm ³										
Grade 4	<500 /mm ³										
Days from the month of the completion of the final regimen	Is calculated using the following formula: date of the initial dose of Adcetris – date of the completion of the final regimen of prior drug										

Term	Definition
of prior drug therapy to the date of 1 cycle of treatment with Adcetris	therapy + 1. If the month of “the completion of the final regimen of prior drug therapy” is missing, the date of the completion of the final regimen of prior drug therapy should be handled as missing.

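### Dose per 3 weeks is a quotient over calendar days, but the SAP classes it at exactly 1.2 and 1.8 mg/kg with no tolerance, so a one-day net shift reclassifies a fully dosed patient

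*SAP*

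**What the plan says.** SAP 4.1 (Treatment given) lists three dose variables: initial dose, mean dose and dose per 3 weeks. All three get the same five classes, "<1.2 mg/kg, 1.2 mg/kg, >1.2 mg/kg to <1.8 mg/kg, 1.8 mg/kg, or >1.8 mg/kg". The same classes return in SAP 5.3, where the percentage of patients with adverse drug reactions is compared across classes with tests and confidence intervals. They return again in SAP 5.9.2, where related peripheral nerve disorders are tabulated by worst grade.

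The definition table in SAP section 1 derives the two computed variables differently:

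- Dose per 3 weeks is "Total “dose of Adcetris”/([“date of the last dose of Adcetris” – “date of the initial dose of Adcetris” + 21)/21". When there is a single cycle ("If only 1 cycle of treatment is given"), the first and last dates are taken as the same.
- Mean dose: "Is calculated as the total value of each dose of Adcetris given at each treatment cycle divided by the number of cycles". No dates enter.

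Neither definition has a rounding rule. BMI, in the same table, does: "The obtained value should be rounded off to one decimal place". SAP 1.2 (Display digits) says of the mean, median and quartiles "The raw data should be rounded off to one decimal place", but that governs displayed summary statistics, not a derived value before it is classified.

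**The concern.** A single-point class suits a prescribed quantity such as the initial dose. Dose per 3 weeks is different: its denominator is a count of calendar days, so it equals 1.8 only when the calendar works out to the day. Small scheduling shifts are to be expected in routine care. Protocol 9.2.5 foresees interruption and restart of treatment, and SAP 5.9.3 and 5.9.8 have a category for interruption or delay.

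At stake is the one variable in SAP 5.3 and 5.9.2 that measures dose intensity over time. Protocol 9.2.5 asks for risk factors and treatment status for peripheral nerve disorders. If the class between 1.2 and 1.8 holds both patients with a one-day slip and patients whose dose was materially reduced, the comparison says little about dose intensity.

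**Working it through.** **Inputs.** Nominal dose and interval, Protocol 5.0: "The usual adult dosage is 1.8 mg/kg (body weight) of brentuximab vedotin (recombinant) infused intravenously once every three weeks". Observation period, Protocol 7.1: "From the start of treatment with Adcetris until the completion of 16 cycles [3 weeks per cycle", so up to 16 cycles of 21 days. Formulas and classes are from the SAP as above. The documents give no expected class sizes, so there is no plan figure to reproduce. They also give no data on intervals between doses.

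**Step 1: dose per 3 weeks when every dose is 1.8 mg/kg.** With n doses and a net shift of D days between first and last dose, last minus first is 21(n − 1) + D. The SAP formula becomes

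1.8 × 21n / (21n + D).

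With D = 0 this is 1.8 for every n, so the formula returns the nominal dose on schedule. For n = 16 and D = 1 it is 1.8 × 336/337 = 1.795.

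| Cycles | 1 day late | 7 days late | 1 day early |
|---|---|---|---|
| 2 | 1.758 | 1.543 | 1.844 |
| 4 | 1.779 | 1.662 | 1.822 |
| 8 | 1.789 | 1.728 | 1.811 |
| 16 | 1.795 | 1.763 | 1.805 |

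Every late value falls in the class between 1.2 and 1.8, and every early value in the class above 1.8. With n = 1 the value is always the dose given. Two full doses with 21 days of delay give 1.8 × 42/63 = 1.2 exactly, so that patient lands in the 1.2 class. The 1.2 class is equally fragile: sixteen doses of 1.2 with one day of delay give 1.2 × 336/337 = 1.196, below 1.2.

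**Step 2: mean dose.** Sixteen doses of 1.8 give 28.8/16 = 1.8 whatever the dates. The value moves only if a dose changes: (15 × 1.8 + 1.2)/16 = 1.7625.

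**Step 3: how far the 1.8 class could thin.** Assume each interval is exactly 21 days with probability q, independently. The share of fully dosed patients with every interval exact is q^(n − 1). Late and early intervals that cancel would add to it.

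| q (assumed) | 4 cycles | 8 cycles | 16 cycles |
|---|---|---|---|
| 0.95 | 86% | 70% | 46% |
| 0.90 | 73% | 48% | 21% |
| 0.80 | 51% | 21% | 3.5% |

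**Step 4: what a tolerance absorbs.** Rounding to one decimal keeps a fully dosed patient at 1.8 while the value is at least 1.75, so D ≤ 21n × (1.8/1.75 − 1) = 0.6n: 2 days at 4 cycles, 4 at 8, 9 at 16. A 5% band keeps values of at least 1.8 × 0.95 = 1.71, so D ≤ 21n × (1.8/1.71 − 1) = 1.105n: 4 days at 4 cycles, 8 at 8, 17 at 16.

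**The case against.** The best reply is that a programmer would round to one decimal, the precision of the class labels. Every one-day delay in the table then returns to 1.8. One week over 8 cycles (1.728) is a real 4% loss of dose intensity, so a lower class is arguably right for it. This stands in part: a stated one-decimal rule would cure the one-day case. But the SAP does not state one. Under it, the one-week slip would round to 1.7 and still share a class with a patient at 1.3.

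The second reply is that dose information appears elsewhere. SAP 4.1 adds continuous summaries, 5.9.3 tabulates actions taken by neuropathy grade, 5.10 lists dose and date for each cycle, and 5.3 and 5.9.2 also use initial and mean dose. All true, and it limits the damage. None of these compares event frequency across dose intensity over time in all patients. SAP 5.3 and 5.9.2 do that, and they use the classes alone.

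The third reply concerns wording: only the net first-to-last shift counts, so a late dose followed by an early one can cancel. That is correct, and the figures above are for net shifts.

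**Conclusion.** The point holds for dose per 3 weeks. As written, the rule misclassifies fully dosed patients with two or more cycles whenever the net shift is not zero, in either direction, and mixes them with patients whose dose was materially lower or higher. The one-day figures are certain arithmetic, given doses of exactly 1.8 mg/kg and unrounded comparison. The thinning figures rest on the assumed q, and range at 16 cycles from 46% to 3.5% remaining.

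A reader might infer two stronger things that the documents do not support:

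- **That mean dose fails in the same way.** It has no time term, so delay cannot move it.
- **That the reference group is emptied, or nearly everyone falls between 1.2 and 1.8.** The SAP names no reference group, single-cycle patients always keep the dose given, and no delay distribution is reported. The documents support a class that can thin, perhaps severely, and no more.

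The overall adverse event frequencies are untouched. The affected results are the dose-per-3-weeks rows in SAP 4.1, 5.3 and 5.9.2.

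**What to change.** For dose per 3 weeks only, in SAP 4.1, 5.3 and 5.9.2, replace the point classes with pre-specified analysis bands around each nominal value. With 5% as an example, the classes become: below 1.14; 1.14 to 1.26; above 1.26 and below 1.71; 1.71 to 1.89; above 1.89 mg/kg. The equivalent percentages of the nominal per-3-week dose would serve as well. State that unrounded values are compared with the limits.

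Keep the existing classes for initial dose and mean dose. The exact 1.8 class of mean dose identifies unreduced treatment, short of deviations that offset each other. A 5% band there would hide real reductions: (14 × 1.8 + 2 × 1.2)/16 = 1.725 would count as full dose.

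The cost is SAP wording and reprogramming on data already collected. The band width is a convention. The band can also absorb a small real reduction: one dose of 1.2 among 16 on schedule gives 1.7625, inside the band. The unchanged mean-dose rows still show it. This concerns data classification only and implies nothing about any dose or schedule.
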